**Table 1. Factors for adjustment**

|  |
|--|
| Age  |
| Sex  |
| COVID-19 status (categorical)  |
| LAPS2 severity of illness measured at the time of hospital admission |
| LAPS2 severity of illness measured at the time of enrollment         |
| ICU admission source   |
| Hospitalization duration prior to ICU admission                      |
| Code status (categorical)  |
| Location of start of MV episode                                      |
| Height   |

If the fitted model violates the 'normality of residuals' assumption, we will use a suitable inference approach such as permutation test or bootstrap confidence intervals. In addition, we will explore alternative modeling approaches to account for non-normality if needed, e.g. two part mixed effects models.

All analyses will be conducted using R (Vienna, Austria).

## VI. Secondary analytic sample

We will repeat the primary analyses using two secondary analytic samples. First, we will include the true ITT population; that is, the entire population of episodes of MV in any study ICU (after exclusions detailed above), regardless of whether or not there was exposure to an implementation strategy during the intervention period. This analysis will provide insight into how ICU-targeted strategies may influence the strategies' effectiveness. We hypothesize that the effect of the strategies to improve administration of low tidal volumes will be attenuated in the true ITT population, compared to the modified ITT population. Second, we will perform a per protocol analysis, restricting the study population to only those episodes where patients were actually exposed to the order panel nudges in the intervention groups and patients who received new orders for mechanical ventilation after the time of ICU transfer in the control group (to identify equivalent patients in the usual care population).

## VII. Analyses of patient-level effect modifiers

Patient-level effect modification will be explored by repeating the analyses of the primary outcomes stratified by four candidate effect modifiers:

- (1) presence or absence of ARDS
- (2) degree of hypoxemia (as measured by the P:F ratio, calculated as the PaO2 divided by the fraction of inspired oxygen (FiO2)).
- (3) Race/ethnicity
- (4) Sex

If differences appear in stratified analyses, we will formally evaluate for effect modification by testing the significance of coefficients for statistical interaction terms between the potential effect modifier and the study groups on the primary outcome of LPV utilization, and on a subset of effectiveness outcomes: in-hospital mortality and hospital length of stay.

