7.2.3. Analyses of patient level factors

Patient-level effect modification will be explored by repeating the analyses of the primary outcomes stratified by the two candidate effect modifiers described in detail above: presence or absence of ARDS and degree of hypoxia (as measured by the P:F ratio, calculated as the PaO₂ divided by the fraction of inspired oxygen (FiO₂)). If differences appear in stratified analyses, we will formally evaluate for effect modification by testing the significance of coefficients for statistical interaction terms between the potential effect modifier and the study groups on the primary outcome of LPV utilization, and on a subset of effectiveness outcomes: in-hospital mortality, hospital length of stay, and sedation measures. Finally, we will conduct subgroup analyses by race/ethnicity and sex/gender to determine the presence of effect modification on outcome.

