After developing a discrete set of clinician factors from interviews (such as level of experience, assigned to ICU versus rotating responsibilities), we will assign them to clinicians and evaluate whether they modify the effects of the implementation strategies quantitatively using the sample of patients cared for by participating clinicians during the trial. To do so, we will first repeat the primary analysis stratified by clinician factors. If we find evidence of differences in the effect sizes, we will add multiplicative interaction terms for each clinician factor with the implementation strategy in the models to quantify whether interactions are significant. To explore the role of ICU factors, we will similarly perform quantitative analyses stratified by ICU. After developing a discrete set of environmental factors from interviews, we will assign them to ICUs and explore whether any patterns emerge.

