## II. Objectives

The trial's overall objective is to compare simple, low-cost, scalable strategies grounded in behavioral economic theory to (a) increase utilization of evidence-based LPV for MV patients, (b) gauge the process-oriented and clinical benefits of targeted vs. non-targeted approaches to changing behavior, (c) explore how clinician and environmental contextual factors affect LPV utilization, and (d) determine how patient factors such as type and severity of disease affect both LPV utilization and its associated outcomes.

Overall, we hypothesize that strategies that encourage clinicians to use LPV among all MV patients will mitigate the aforementioned barriers of knowledge gaps and diagnostic uncertainty, thereby increasing LPV utilization across diverse settings among patients with and without ARDS.

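### Interaction terms are fitted only if primary-outcome strata look different, so similar-looking modifiers get no interaction estimate and mortality and length-of-stay interactions may go unexamined

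*SAP*

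**What the plan says.** SAP VII begins: "Patient-level effect modification will be explored by repeating the analyses of the primary outcomes stratified by four candidate effect modifiers". The four are ARDS, P:F ratio, race/ethnicity and sex. The stratified analyses carry no condition. The interaction models do: "If differences appear in stratified analyses, we will formally evaluate for effect modification by testing the significance of coefficients". The same sentence applies these tests to the primary outcome and also "on a subset of effectiveness outcomes: in-hospital mortality and hospital length of stay".

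Protocol 7.2.3 has the same wording ("If differences appear in stratified analyses, we will formally evaluate for effect modification") for two modifiers, ARDS and degree of hypoxia, and adds sedation measures to the outcomes. It treats race and sex separately and without the condition: "Finally, we will conduct subgroup analyses by race/ethnicity and sex/gender to determine the presence of effect modification on outcome". Protocol 7.2.4 follows the same logic for clinician factors: "If we find evidence of differences in the effect sizes, we will add multiplicative interaction terms for each clinician factor".

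Neither document gives a threshold for a difference, says who judges it, or plans an interaction test that is run in any case. Objective (d) in SAP II, repeated in Protocol 2.1, is to "determine how patient factors such as type and severity of disease affect both LPV utilization and its associated outcomes". SAP XIV.a gives power for effect-modification analyses as one reason for not stopping early for effectiveness.

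**The concern.** A test that is run only after a look at the data it will use has a p-value that is hard to read. The reader sees interaction tests for the modifiers that looked different and does not know how different they had to look. For modifiers that looked similar, the reader gets stratum estimates but no estimate of their difference and no interval to show which differences remain plausible. Separate stratum estimates do not supply that interval.

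The condition also reaches across outcomes. The look is at the primary outcomes, which are tidal-volume measures, yet it decides whether interactions on mortality and length of stay are examined. A patient factor could alter the effect on mortality without altering the effect on ventilator settings. Objective (d) asks about both, at least for type and severity of disease.

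**Working it through.** The documents state no power, alpha or sample size for the interaction analyses, so there is no figure of theirs to reproduce. The numbers below illustrate what the condition does.

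**Assumptions, none of them in the documents.** Interaction tests are two-sided at 0.05. The estimated interaction is approximately normal. A difference is judged to appear when the estimate exceeds c standard errors, with c = 0.5, 1 or 1.5.

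**1. Same contrast, no true interaction.** Every result with |Z| > 1.96 has also passed |Z| > c, so the share significant among tests that are run is 0.05 / P(|Z| > c).

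| c | P(test is run) | Significant among tests run | Significant overall |
|---|---|---|---|
| 0.5 | 0.617 | 0.05/0.617 = 0.081 | 0.05 |
| 1.0 | 0.317 | 0.05/0.317 = 0.158 | 0.05 |
| 1.5 | 0.134 | 0.05/0.134 = 0.37 | 0.05 |

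The last column is constant: the false positives are the same, over a smaller denominator.

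**2. Four intervention groups.** Each two-level modifier has four interaction coefficients (A, B, A+C, B+C). Suppose all four are tested when any one exceeds 1 SE. By simulation under no interaction, the screen is passed in 78% of cases if the coefficients are independent, and 71% if their correlation is 0.5. At least one is significant in 24% or 22% of the cases tested, against 18% or 15% with no screen. The pattern is the same, but weaker.

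**3. Same contrast, real interaction with expected Z = 2.** The probability of failing the screen is Φ(c − 2) − Φ(−c − 2):

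- c = 0.5: 0.067 − 0.006 = 0.061
- c = 1.0: 0.159 − 0.001 = 0.157 (before rounding the terms)
- c = 1.5: 0.309 − 0.000 = 0.308

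None of these results would have reached 1.96, so no power is lost on this contrast. What is lost is the estimate and its interval.

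**4. Screen on the primary outcome, test on mortality or length of stay.** Suppose a factor modifies the mortality effect but not the tidal-volume effect. With a single-contrast screen, the mortality interaction is examined with probability P(|Z| > c). It is left out in 1 − 0.617 = 38%, 1 − 0.317 = 68% or 1 − 0.134 = 87% of trials. With the four-coefficient screen at 1 SE it is left out in 22% or 29%. Here power is lost. If the tidal-volume and mortality statistics are close to independent, the tests that are run keep roughly their nominal 5%, so the shares in step 1 do not apply.

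**5. The two documents side by side.**

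| | Protocol 7.2.3 | SAP VII |
|---|---|---|
| Modifiers under the condition | ARDS, hypoxia | ARDS, P:F ratio, race/ethnicity, sex |
| Race and sex | Subgroup analyses, no condition, no interaction test stated | Under the condition |
| Outcomes besides LPV use | Mortality, hospital stay, sedation | Mortality, hospital stay |

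**The case against.** The strongest defence is that the condition does little harm where it can be measured. On the same contrast it creates no extra false positives. The four modifiers are named in advance, so a reader knows the full list against which any reported interaction should be judged. Stratum-specific effects on the primary outcome are planned for every modifier, whatever they look like. The SAP describes the work as exploration of candidate modifiers, and the primary hypotheses in SAP V.b do not include it. All of this stands.

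It also rules out several stronger readings that a reader might infer. One is that the condition inflates type I error; step 1 shows that it does not. Another is that subgroup findings are picked after the fact; the modifiers are fixed and only the formal test is conditional. A third is that untested modifiers are left with no result; for the primary outcome they still have stratum estimates. A fourth is that objective (d) covers all four modifiers; it gives type and severity of disease as its examples, which fit ARDS and P:F ratio, and does not name race or sex.

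The defence does not justify the condition itself. It is undefined, it withholds the interval that a reader needs for a modifier that looks similar, and it makes interactions on clinical outcomes depend on a different outcome. SAP VII states no stratified analysis for mortality or length of stay to fall back on.

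**Conclusion.** The point holds as a minor one about reporting and pre-specification. The primary comparisons are not affected.

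The 8%, 16% and 37% describe only true-null interactions that pass a screen on the same contrast, under assumed thresholds of 0.5, 1 and 1.5 SE and an assumed 0.05 level. Their spread shows that a reported p-value cannot be read without knowing the screen. The more substantial loss is in coverage: similar-looking modifiers have no interaction estimate or interval, and mortality and length-of-stay interactions may never be fitted. The probability of that last omission depends on how the look is made. In the illustrations it ranged from about 22% to 87% when the factor does not modify the primary outcome. The case is clearest for ARDS and P:F ratio, because objective (d) names type and severity of disease and their effect on outcomes.

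**What to change.** In SAP VII and Protocol 7.2.3:

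- Delete the condition. Fit the interaction model for all four pre-specified modifiers on the primary outcome, in-hospital mortality and hospital length of stay, whatever the stratified results.
- Report every interaction estimate with its confidence interval, and use the stratified estimates as description.
- Label these analyses exploratory, or state a multiplicity rule. The Holm procedure in SAP IX covers the between-arm contrasts, and no rule is given for interactions.
- State whether P:F ratio enters as a continuous variable or with fixed cut-points.
- Reconcile the two documents on which modifiers are included and whether sedation measures are among the outcomes.

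The cost is a few more models on data already collected, and more reported tests. With one coefficient per modifier and intervention group there would be 4 × 4 × 3 = 48, of which 48 × 0.05 = 2.4 would be expected to be significant at 0.05 if no interaction existed. That is why the exploratory label or a multiplicity rule should come with the change.

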## VIII. Subgroup analyses

In addition to the analyses above of patient-level effect modifiers, we will perform the following pre-specified subgroup analyses:

1. Patients without COVID-19, because we have observed that adherence to low tidal volume ventilation is high among patient with COVID-19 and there will likely be little or no effect from the study interventions.
2. Patients in the ITT group who are excluded from the MITT group. These patients would be eligible for exposure only to the RT-targeted intervention, as by definition they would not have been exposed or eligible for exposure to Strategy A or B if they did not have a new order for MV placed after ICU admission. In this subgroup, the exposure variable will be exposure to Strategy C (based on the time of admission to the study ICU relative to the ICU's intervention status with regards to Strategy C).

## IX. Sensitivity analyses

- a. **Time effect might differ across clusters:** To account for the possibility that the time effect might not be the same for all clusters, we will add a random interaction term for the cluster-time combination  $\varphi_{ij}$ .
- b. **Treatment effect might differ across clusters:** To evaluate the possibility of treatment-effect heterogeneity, we will add a random interaction term  $X_{ij}\tau_i$  which allows different treatment effects for different clusters.
- c. **Exclusion of subsequent MV episodes in patients with multiple MV episodes may lead to bias estimates of effect:** To address potential bias of excluding subsequent episodes of MV among patients who undergo multiple episodes, we will repeat the primary analysis including all eligible episodes of MV.

d. **ICU may be a potential confounder.** Because the study ICU may itself be a potential confounder, we will repeat analyses modeling the study ICU as a fixed effect.

In order to preserve an overall family wise error rate of 0.05, we will pre-specify a type I error rate threshold for the comparison of A vs. B at 0.025, and will estimate the Holm thresholds for the remaining comparisons by ordering unadjusted p-values (from the smallest to largest), and then calculating it as 0.025 divided by n remaining contrasts.

## X. Secondary Outcomes and Potential Adverse Effects

We will analyze several secondary measures of implementation, effectiveness, and potential adverse effects, as listed in **Table 2**.

**Table 2 Secondary outcome measures**

| Implementation Outcomes  | Variable coding | Definition  |
|---|------------------------|--|
| 
 
Total duration of exposure to tidal volume >8 cc/kg and >10 cc/kg IBW
 
 | Continuous             | In hours; exclude time on minimal settings; report for first 72h after enrollment and for entire duration of MV episode within a study ICU   |
| 
 
Initial tidal volume administered
 
   | Continuous             | In cc/kg IBW; exclude time on minimal settings; report the first documented tidal volume at or after the time of enrollment  |
| 
 
Plateau pressure (Pplat) >30cm H2O at time 0 and time 24h
 
                | Binary                 | Time 0 is the earliest measure between 0 and 6h; time 24 is the measure between 18h and 30h that is closest to 24h and earliest if there are two measures of the exact same distance from 24h (e.g., one before and one after) |
| Effectiveness Outcomes   |                        |  |
| 
 
Hospital mortality
 
  | Binary                 | Vital status at hospital discharge   |
| 
 
Hospital discharge disposition
 
  | Categorical            | To be collapsed into 4-6 categories  |
| 
 
Duration of MV
 
  | Continuous             | From time of enrollment to end of MV in study ICUs, up to 30 days  |
| 
 
ICU length of stay
 
  | Continuous             | From time of enrollment to end of admission to enrolling ICU, up to 30 days  |
| 
 
Hospital length of stay
 
   | Continuous             | From time of enrollment to time of hospital discharge, up to 30 days   |
| Potential Adverse Effects  |                        |  |
| 
 
Early deep sedation
 
   | Continuous             | Proportion of time during the first 72 hours of mechanical ventilation that patients were alive, in the ICU, and with Richmond Agitation-Sedation Scale (RASS) of -3 to -5   |

|  |            |  |
|--|------------|--|
| • Average sedation intensity within the first 72 hours                           | Continuous | Average RASS value, weighted by duration of time at that value   |
| • Deep sedation for the entirety of the first 72 hours of mechanical ventilation | Binary     | Whether the patient was kept at RASS -3 to -5 for the entirety of the first 72 hours of mechanical ventilation |

We will define duration of MV per episode as:

[Time 1: time of discontinuation of MV, up to 30 days after Time 0] – [Time 0: time of first eligibility]

We will define ICU length of stay as:

[Time 1: time of discharge from study ICU, up to 30 days after Time 0] – [Time 0: time of enrollment]

We will define hospital length of stay as:

[Time 1: time of hospital discharge, up to 30 days after Time 0] – [Time 0: time of enrollment]

Measures of excessive sedation as a potential adverse consequence of LPV will be defined as above in **Table 2**.

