1.1 Background and rationale for the INPUT study

Of the million Americans who undergo invasive mechanical ventilation (MV) annually within intensive care units (ICUs),¹⁻³ 30-35% die in the hospital,^{1,4} and survivors commonly have long-term cognitive, emotional and physical impairments.^{5,6} Although potentially life-saving, MV can also injure the lungs.⁷ Strategies of “lung-protective ventilation” (LPV) aim to minimize harm by delivering low tidal volumes (the amount of air per breath delivered by the ventilator) and limiting the artificial pressures in the lungs. LPV was first proven effective in patients with acute respiratory distress syndrome (ARDS), a severe form of respiratory failure associated with pneumonia, sepsis, and other common illnesses.⁸ A multicenter randomized trial published in 2000 demonstrated an absolute mortality reduction of 10%, shortened duration of MV, and reduced organ failure rates.⁹ These findings have since been replicated and incorporated into international guidelines.¹⁰ However, over fifteen years later, more than one-third of ARDS patients overall, and up to 81% in some ICUs, do not receive LPV.^{11,12}

Multiple studies across diverse ICUs have consistently identified two key barriers to LPV utilization: limited knowledge about LPV,¹³⁻¹⁷ and tendencies to prescribe LPV only when ARDS is definitively diagnosed,^{14,15} in part due to theoretical concerns about potential harms of LPV.¹⁵ However, definitive diagnosis of ARDS is challenging.^{18,19} And recent evidence suggests that (1) concern for harm among patients without ARDS is likely unwarranted,^{20,21} and (2) LPV may in fact reduce lung injury and mortality even among patients without ARDS.²²

2. Objectives

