3.9.2 Secondary outcome variable(s)

We will include additional measures of LPV as secondary implementation outcome measures:

- Durations of exposure to tidal volume >8 cc/kg ideal body weight
- Duration of exposure to tidal volume >10 cc/kg ideal body weight
- Initial tidal volume administered
- Initial plateau pressure (Pplat)

We will also evaluate the following clinical outcomes:

- In-hospital mortality
- Hospital discharge disposition
- Duration of MV
- ICU length-of-stay
- Hospital length of stay

We will evaluate the potential adverse effect of excessive sedation with LPV using the following additional secondary outcome measures:

- Early deep sedation, defined as the proportion of time during the first 72 hours of mechanical ventilation that patients were alive, in the ICU, and with a RASS -3 to -5
- Average sedation intensity within the first 72 hours, defined as the average RASS value, weighted by duration of time at that value
- Deep sedation for the entirety of the first 72 hours of mechanical ventilation (binary)

4. Trial Implementation

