## V. Primary outcome and analytic method

### a. Primary outcome

The primary outcome variables will be (1) **fidelity** to LPV, measured by the percentage of time in the first 72 hours of mechanical ventilation that a patient is exposed to tidal volume  $\leq 6.5$  cc/kg ideal body weight and (2) **sustainability** of the effects of the implementation strategies, measured as the percentage of time in the first 72 hours of MV that a patient is exposed to tidal volume  $\leq 6.5$  cc/kg ideal body weight among MV patients each month during 6 months after the study monitoring period ends.

We will consider episodes separated by less than or equal to 2 hours as a single episode. We will count the period of time that a patient is extubated as if the patient is on minimal settings, and will therefore subtract that period of time from the denominator of the primary outcome variable (if it falls in the first 72 hours).

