### c. Primary analytic sample

For the purpose of the trial, the **primary analytic sample** will be limited to episodes of MV among patients who meet the following criteria:

1. Aged 18 and over; **AND**
2. Admission to 1 of the 12 participating ICUs; **AND**
3. Undergoing mechanical ventilation

Any episodes of MV that meet the eligibility criteria above will be **excluded** from the primary analysis if they meet any of the following criteria:

1. The episode of MV lasts less than 12 hours, because we believe that the evidence-based practice may not apply to these patients nor alter their outcomes.
2. The patient is on minimal settings for the entirety of MV, defined as a spontaneous mode (e.g., pressure support ventilation) with pressure support  $\leq 10$  cmH2O, **AND** PEEP  $\leq 8$  cmH2O, **AND** FiO2  $\leq 50\%$ , because the clinical significance of spontaneous tidal volumes is unknown and low tidal volumes may not be beneficial or desirable.
3. Goals of care are documented as comfort measures only (as identified by presence of an order for “Comfort Care” in the EHR) during the first 72 hours during episode of MV, because mechanical ventilation is managed differently during care focused exclusively on comfort and low tidal volume ventilation may not be appropriate, nor would it likely influence clinical outcomes.
4. There is no height documented in the EHR at the time of initiation of MV, because we will be unable to estimate ideal body weight, a necessary parameter to calculate the primary outcome, and because they will not receive the interventions.
5. The height documented is less than 4 feet, because the formula for ideal body weight does not hold true below this height.

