### a. Analysis of secondary outcomes

Secondary implementation outcomes will be analyzed at the level of the episode and will be modeled as per the primary analysis, using generalized linear mixed effects models, with appropriate links for binary and categorical dependent variables.

For example, for a binary outcome, the model has the form

$$\text{logit}(Y_{ijk}) = \mu + \alpha_i + \beta_j + X_{ij}\theta$$

Model parameters are similar to those in the primary outcome analysis.

Effectiveness outcomes and potential adverse effects will be analyzed at the level of the episode of MV. Binary and categorical effectiveness outcomes (mortality and discharge disposition) will be modeled per the primary analysis.

For MV duration, ICU length of stay, and hospital length of stay, because of a high mortality rate (~30%), we will model these outcomes as a composite with death using a “free days” approach. In other words, for duration of MV, for example, we will use ventilator-free days within 30 days, which will be calculated as the number of days a patient is alive and not on invasive mechanical ventilation for 30 days from the start of enrollment. We will use similar calculations for ICU-free days (alive and not admitted to the study ICU) and hospital-free days (alive and not admitted to the study hospital). For patients who are discharged alive and off the ventilator prior to 30 days, we will assume they are alive and off the ventilator for the remainder of 30 days. For patient who are discharged on the ventilator prior to 30 days, we will assume they remain on the ventilator for the remainder of 30 days. For patients who are discharged to hospice (home or facility), we will assume they have died upon the day of discharge.

We will explore the population where patients have multiple episodes of MV, as patients with multiple admissions may have higher risk of mortality. We will also examine the patient outliers in terms of MV

duration, ICU length of stay and hospital length of stay. Depending on the proportion, we may include multiple episodes into the study by creating a variable about the number of episodes.

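### Exposure above 8 and 10 cc/kg is listed as an implementation outcome in total hours, so it moves with ventilated time as well as with practice; a share of ventilated time should carry the implementation reading

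*SAP*

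**What the plan says.** Table 2 in SAP section X places total exposure above 8 and above 10 cc/kg ideal body weight under Implementation Outcomes, as a continuous variable: "In hours; exclude time on minimal settings; report for first 72h after enrollment and for entire duration of MV episode within a study ICU". Protocol 3.9.2 uses the same scale ("Durations of exposure to tidal volume >8 cc/kg ideal body weight", with a matching line for 10 cc/kg), as does the Protocol Summary.

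On the model, SAP X.a states: "Secondary implementation outcomes will be analyzed at the level of the episode and will be modeled as per the primary analysis". It adds no offset for ventilated time. The adjustment factors in SAP Table 1 include time in hospital before ICU admission but not time ventilated.

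Other outcomes in the plan are scaled to time, or deal with death explicitly:

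- The primary outcome (SAP V.a) is "measured by the percentage of time in the first 72 hours of mechanical ventilation that a patient is exposed to tidal volume" at or below 6.5 cc/kg. For a short extubation between merged episodes, the SAP will "subtract that period of time from the denominator of the primary outcome variable", because it treats that time as minimal settings.
- Early deep sedation (SAP Table 2) is "Proportion of time during the first 72 hours of mechanical ventilation that patients were alive, in the ICU", at the specified sedation depth.
- Duration of ventilation, ICU stay and hospital stay (SAP X.a) are analysed as free days combined with death, because mortality is put at about 30%.

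**The concern.** An implementation outcome should show whether clinicians set the ventilator differently. Total hours answer a different question: how much high-volume ventilation the patient accumulated. That depends on the settings and also on how long the patient was alive, ventilated, in the study ICU and off minimal settings. All of these are determined after the strategy is in place, and two of them, mortality and duration of ventilation, are effectiveness outcomes in the same table.

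If an arm had shorter ventilation, more early deaths or more early ICU exits, its hours would fall and could be read as better practice. If an arm had longer survival on the ventilator, its hours would rise and could be read as worse practice. Excluding time on minimal settings does not remove this, since hours still scale with the remaining time, and an earlier move to minimal settings also lowers them. What is at stake is the interpretation of two listed secondary results.

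**Working it through.** The documents give no expected value, sample size or power for these two outcomes, so there is no plan figure to reproduce. The check applies the definition itself. All shares and durations below are assumptions.

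**Inputs from the documents.** The unit is hours, in two windows (first 72 h and whole episode in a study ICU), without minimal-settings time (SAP Table 2). The exclusion "The episode of MV lasts less than 12 hours" (SAP V.c) means eligible episodes can be as short as 12 h, well inside the 72 h window.

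**Identity.** Let s be the share of non-minimal ventilated time above the threshold and T the non-minimal ventilated hours observed. Whole-episode hours = s × T. Hours in the 72 h window = s × min(T, 72), when s is constant over the episode.

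**1. Single episodes, s = 20%.**

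- T = 12 h: 0.20 × 12 = 2.4 h
- T = 24 h: 0.20 × 24 = 4.8 h
- T = 72 h: 0.20 × 72 = 14.4 h
- T = 120 h: 24.0 h whole episode, 14.4 h in the 72 h window

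With s from 10% to 30%, a 12 h episode scores 1.2 to 3.6 h and a 72 h episode 7.2 to 21.6 h. These compare individual patients; steps 2 and 3 compare groups.

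**2. Two arms with the same practice (s = 20%) and different mean ventilation.** Assume T = 12 h plus an exponential variable, with overall mean m. Then E[min(T, 72)] = 12 + (m − 12)(1 − exp(−60/(m − 12))). For m = 120: 12 + 108 × (1 − exp(−60/108)) = 58.0 h, and 0.20 × 58.0 = 11.6 h.

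| Mean T, arm 1 / arm 2 (h) | Whole-episode hours | Change | Hours in 72 h | Change |
|---|---|---|---|---|
| 120 / 108 | 24.0 / 21.6 | −10% | 11.61 / 11.32 | −2.4% |
| 120 / 96 | 24.0 / 19.2 | −20% | 11.61 / 10.98 | −5.4% |
| 96 / 72 | 19.2 / 14.4 | −25% | 10.98 / 9.99 | −9.0% |
| 144 / 96 | 28.8 / 19.2 | −33% | 12.04 / 10.98 | −8.9% |

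The share is 20% in every cell, so an analysis of the share would show no difference. The percentage changes do not depend on the value of s.

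**3. Early death or ICU exit, 72 h window.** Suppose an extra fraction d of episodes in one arm end at 24 h instead of lasting 72 h or more. The mean falls by d × 0.20 × (72 − 24) = 9.6d hours: 0.19, 0.48 and 0.96 h for d = 2%, 5% and 10%. That is 1.3%, 3.3% and 6.7% of the 14.4 h that a full window scores.

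**4. Masking.** Let practice worsen from a 20% to a 25% share while ventilation shortens from 120 to 84 h. Whole-episode hours go from 0.20 × 120 = 24.0 to 0.25 × 84 = 21.0. The hours improve while practice deteriorates.

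**5. Does a share remove the problem?** Not entirely. Assume 40% of time above 8 cc/kg in the first 24 h and 10% afterwards, for everyone. A patient stopped at 24 h has 9.6/24 = 40%. A patient ventilated for 72 h has (9.6 + 4.8)/72 = 20%. The share is free of duration only when exposure is roughly constant over the window.

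**The case against.** The strongest reply is that cumulative hours are a deliberate and coherent quantity. The Protocol Summary, Protocol 3.9.2 and SAP Table 2 all describe a duration, and Protocol 1.1 says that ventilation can injure the lungs, so total time at high volume is a sensible injury dose. This stands: hours should be kept. It does not make hours a measure of clinician behaviour, which is how Table 2 classifies them.

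Second, practice is measured elsewhere without this dependence on accumulated time: by the primary percentage, the initial tidal volume, and plateau pressure at fixed times. Mortality and ventilator-free days are also reported, so an attentive reader could see a shift in duration. This stands, and it limits the weight of the point.

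Third, a reader might infer that the plan expects shorter ventilation, so that the hours will flatter the strategies. The documents do not support that. Protocol 1.1 lists "shortened duration of MV, and reduced organ failure rates" among the results of a past trial in ARDS. This trial enrols ventilated patients generally, and its primary hypotheses (SAP V.b) concern utilization only. The power sections also consider lower hospital mortality, which would tend to lengthen time at risk. The net direction is unknown.

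Fourth, early death is partly limited by the exclusions for episodes under 12 h and for comfort care in the first 72 h, and the mortality of about 30% is not a 72 h rate. This also stands; the documents give no 72 h figure, so the fractions in step 3 are only illustrative.

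**Conclusion.** The point holds as a limit on interpretation. As written, the two outcomes combine practice with time at risk, and no denominator, offset or rule for death or ICU exit separates them. With equal shares and the assumed durations, the spurious change is 10% to 33% for whole-episode hours and about 2% to 9% for the 72 h version. Bias between arms arises only if ventilated time, death, ICU exit or time on minimal settings differs between arms.

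Two stronger readings should be resisted. A reader might take a given percentage shortening of ventilation to produce the same percentage fall in both windows; the 72 h cap makes the effect there much smaller. A reader might also conclude that the trial's main result is compromised; it is not, because the primary outcome is a percentage of time with its own denominator, and no conclusion in the documents is tied to the hours outcomes. The change below is an inexpensive improvement, not the repair of an error.

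**What to change.** In SAP Table 2, add the percentage of non-minimal ventilated time in the first 72 h above 8 cc/kg, and the same above 10 cc/kg, with the primary outcome's denominator and model. State that these are the forms interpreted as implementation.

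Keep the pre-specified hours in both windows. Report them as cumulative dose, beside mortality and ventilator-free days, and state that they are not read as evidence of practice change.

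The protocol version is dated 07/20/2023, and SAP XIV.c places completion of the trial in May 2023. If group comparisons have already been run, label the share as added later.

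The cost is small: the same data, two added measures, and matching wording in the Protocol Summary and Protocol 3.9.2. The hours would no longer carry the implementation claim. The share can still vary with duration if high-volume exposure is concentrated early, and the report should say so.
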